Target number of participants	We anticipate to recruit 800 participants for this study over the course of 4 years

Criteria for evaluation	
Primary outcome measure(s): The primary outcome of the study is to evaluate if specific heritable arrhythmic disorders are associated with changes in selected protein distribution/expression levels at cell-cell junctions within the buccal mucosa. Our preliminary studies suggest that protein distribution/expression alterations in the buccal mucosa mirror equivalent changes that occur in the myocardium of patients with ACM. This study will evaluate the use of this "novel diagnostic tool" in individuals at risk of sudden cardiac death due to other, more common forms of arrhythmic disorders including the cardiac channelopathies. The processing approach (laboratory technique: immunocytochemistry) for protein distribution visualization has been optimized to be qualitative rather than quantitative. In this sense - each sample will be characterized by "presence" or "absence" of a specific protein at the cell-cell connections. We deem that the qualitative approach is not subject to bias and will ensure accuracy and reproducibility of the results.
 
Secondary outcome measure(s): A potential secondary outcome of the research is whether we can correlate protein distribution in the buccal mucosa with specific genotypes. Our preliminary results on the cohort of patients with ACM suggest that mutations in different genes result in different protein distribution patterns within the buccal mucosa. Being able to predict the gene bearing the disease-causing mutation will significantly reduce the time and cost of genetic sequencing. Identifying the specific gene underlying a heritable arrhythmic disorder is of pivotal importance as increasingly developing genotype/phenotype correlations help individualized risk identification and patient management.
 
Another potential secondary outcome of the research has to do with the effect changes in the patients' treatment plans may have on protein distribution. An example has to do with a protein known as Connexin43 (Cx43). Cx43 is the major gap junction protein expressed in the heart and is responsible for the electrical coupling of the cells and the smooth propagation of electricity throughout the myocardium. Cells at the buccal mucosa also express Cx43. It has been shown that patients with arrhythmic disorders show decreased distribution of Cx43 at the cell borders in their hearts and this "Cx43 remodeling" has been associated with an increased risk for arrhythmias. Our preliminary studies show that patients with ACM, as well as patients with different types of cardiomyopathy (including dilated, hypertrophic and ischemic) show Cx43 remodeling in their buccal mucosa. If a patient shows Cx43 remodeling during initial sampling and in a follow-up visit his clinical care team deems necessary to change his treatment plan (for instance, if he/she is to be started on a different anti-arrhythmic drug) we would like to study Cx43 distribution again during one of his/hers follow up visits. If the new treatment plan results in restoration of Cx43 at the buccal mucosa cell connections, and given how protein distribution in the buccal epithelium mirrors protein distribution in the heart, this finding may be an indication of successful arrhythmia management. It could thus, potentially, provide us with a non-invasive, straightforward and risk-free means to assess therapy efficacy in the future.

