All participants that are screened for inclusion into the study must be entered onto the Sponsor screening log JREOLOG0001 and will be assigned a unique study sequential number. Participants will be considered eligible for enrolment into this trial if they fulfil all of the inclusion criteria and none of the exclusion criteria as defined below.

Eligible participants will be entered onto the Sponsors Subject ID log JREOLOG0002 and assigned a unique study specific Identification number in a pre-agreed format in accordance with Site identifier and next sequential numerical value e.g. SG001

Inclusion criteria

- Participants will include patients diagnosed with a heritable arrhythmic disorder (including arrhythmogenic, hypertrophic and dilated cardiomyopathy, cardiac sarcoidosis as well as cardiac channelopathies; Long QT syndrome, Brugada syndrome and catecholaminergic polymorphic ventricular tachycardia).
- Family members of victims of SCD evaluated at the same clinic for risk assessment and diagnosis. These groups include both individuals with clear disease manifestation (termed "affected") as shown by conventional diagnostic approaches (electrocardiography, echocardiography, cardiac MRI, Holter monitoring) as well as potential carriers of disease-causing mutations who, however, may not/not yet manifest any overt sign of cardiovascular abnormalities (termed "carriers"). These are typically family members of probands diagnosed with a heritable arrhythmic disorder or family members of a sudden cardiac death victim.
- All individuals that fall in the above categories will be included regardless of their management (medication, devices, and surgical procedures).
- Individuals with co-existing conditions will also be included and their medical history will be taken into account when interpreting the results of the immunohistochemical or Western immunoblotting analysis.
- Adult individuals (>18 years of age).
- Pregnant women will be included as the approaches used is not in any way harmful or uncomfortable.
- All individuals must have provided the study team with a signed informed consent in order to participate in the study.

Exclusion criteria

- Children under 18 years of age
- Individuals lacking decisional capacity.
- Individuals with non-heritable, non-arrhythmic cardiac disorders (such as ischemic heart disease or inflammatory disorders).

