Regardless of the outcome of the baseline analysis, all participants will be asked to provide the study team members with additional samples up to 3 times/year following their appointment, using a self-sampling kit, and then at their next regular follow-up appointment. If the interim results yielding from the analysis of the self-obtained samples, shows abnormal protein distribution, the medical providers may contact the participant and discuss with them the possibility of bringing their next regular appointment forward for discussion and further evaluation. Regarding the sub-study, the majority of participants will only be asked to provide buccal cells once. In selected cases we may invite them to provide an additional sample at their next regular appointment. Our buccal smear work has shown that one protein in particular, Connexin43, shows restored distribution in response to clinically effective anti-arrhythmic medication. Yet, to date, we do not know what is the mechanism of action through which drugs fix Connexin43 localization and hence restore normal cardiac rhythm. Our sub-study would show whether the drugs act by increasing protein production or merely shifting the protein to junctional sites facilitating electrical conduction.

Methods

Laboratory procedures (if applicable)

The samples obtained will be mailed to [name] research laboratory. The fixed slide will be dipped in blocking buffer (97 ml phosphate buffered saline (PBS), 3 ml normal goat serum, 1 gram of bovine serum albumin and 150 microliters of Triton-X for a total of 100ml). The slides shall be left to incubate for 45 minutes at room temperature. The primary antibody will then be added (I use a liquid-repellent pen to draw a circle around the area where the cells are) diluted in blocking

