No samples will be shipped outside [name] laboratory. Following imaging, the samples will be stored at a 4 °C fridge in [name] laboratory and they shall be safely discarded at the end of the study. All samples will be de-identified; there shall be no way to link a particular slide with a specific patient. No sample will be used for any further study other than the one described in the information sheet. A study ID log containing participants name and unique study identification number will be kept separately from any other information related to the study in the ISF. Any samples and test results will only bear the unique participant ID number. To ensure data confidentiality, only authorized persons will be granted access to study data, passwords and system IDs shall not be shared, physical security of the workstations/files will be maintained, adequate back-up plans will be in effect and staff will be trained on data entry systems and importance of security procedures. Only the participants' direct care team will have access to personal data or medical files throughout the duration of the study. Professional auditors and regulatory inspectors (NHS offices) may need to get access to participants' information to ensure the study is compliant with regulations. The participants will be informed of this possibility by their medical care providers, it shall be stated on the information sheet and they will consent to it as part of their informed consent.

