The data will be stored in TIF (images) format. The observations of the images will be logged on excel spreadsheets. City St George's, University of London is developing an institutional data repository as part of a Jisc-funded RDM Shared Service (April 2016 - September 2017). This will provide discoverability, secure storage and long-term preservation for all research data deposited in it. The PI will not have access to patient data/medical records. Slides will be labelled by a unique study participant ID code. There shall be no hard copy of the key linking the code to patients kept in the laboratory. There will be a linked document stored in the ISF JREOLOG0002. The study will be conducted in compliance with SOPs, GCP, all relevant laws of the EU and the UK including but not limited to: the Human Rights Act 1998, the Data Protection Act 1998, the Human Medicines Regulations 2012, ICH, the World Medical Association Declaration of Helsinki (2008), the NHS Research Governance Framework for Health and Social Care (2005). At the end of the study all coded samples shall be disposed of in accordance with the Human Tissue Authority's code of practice. Data generated will be kept on a password-protected workstation within a controlled-access office at City St George's, University of London. Computer softwares and firewall protection are up to date. City St George's, University of London servers are protected by line-interactive uninterruptible power supply (UPS) systems. No data will be kept in cloud-based storage. Only secure City St George's, University of London -controlled FTP servers will be used to share data with other team members. No sensitive data will be emailed according to ISO 27001. Digital data kept on City St George's, University of London servers are backed up overnight, every night, to hard disk and then cloned to tape storage. Full backups of all the data will be carried out monthly. The cloned tapes are stored separately in a fireproof and bombproof safe off-site. Laptops will be backed up and data removed from them as soon as practicable. This is in accordance with the City St George's, University of London Information Security and Removable Media policies: <https://portal.sgul.ac.uk/org/lis/computing-services/infosec-external>

Archiving arrangements

The trial essential documents along with the trial database will be archived in accordance with the sponsor SOP JREOSOP0016. The agreed archiving period for this trial will be 10 years.

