- Research is not used to make decisions directly affecting individuals
- Short retention limits
- Restricted access controls
- Other (please specify)

Samples will be identified by a study ID number only. No personal data will be noted on the slides.

A key linking the study ID numbers to specific individuals will be kept in protected workstations at respective hospital sites only accessible by the participants' regular medical team.

How long will you need to hold the personal data for after the study has completed?

Not applicable

How will you make sure that you are holding data for the appropriate length of time and no longer?

Not applicable

How will the data be held /stored?

Personal data for all patients/family members are routinely held in medical files and electronically by the individuals' regular medical care providers. There shall not be shared with the principal investigator.

Will you be using any electronic and/or paper Case Report Forms (CRFs) to collect data? If so what are these and how will they be held securely and managed at the end of the project?

A data collection form, not including any personal data, will accompany each set of slides or cell suspension sample. This will include:

- The arrhythmia syndrome the participant has been diagnosed with

- Whether the participant has a family history of sudden cardiac death
- Whether the participant is taking any regular medication
- Whether the participant has been diagnosed with additional medical conditions
- Whether the participant is bearing a known disease-causing mutation
- The number of slides obtained (or if participating in the sub-study whether a single or double round of toothbrush rubbing was required to obtain sufficient cells)
- The team member obtaining the smears/cell sample (or the participant if using the at-home kit)

These will be completed by the participant's regular medical providers.

Following completion of the immunohistochemical/western immunoblotting analysis the principal investigator will complete the second part of the form with any changes observed in the distribution/expression levels of key proteins investigated.

There shall be no personal data noted on the form.

The forms will be held in [name] office at City St George's, University of London. The office is locked and accessible only by the PI.

Upon completion, they shall also be scanned and an electronic copy held in [name] St George's, University of London workstation accessible by the PI only.

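### Repeat samples keep the participant's single enrolment ID and nothing masks earlier results, so a reader can know the previous call when judging whether Cx43 is restored

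*Combined protocol and SAP*

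**What the plan says.** - **ID.** Under section 7 (Participation selection criteria), eligible participants are "assigned a unique study specific Identification number in a pre-agreed format in accordance with Site identifier and next sequential numerical value". The example given is a site prefix followed by a number.
- **Labels.** Section 10.5.1 states: "Any samples and test results will only bear the unique participant ID number". It repeats the rule for the sub-study tubes. Section 12.4 (Data handling and analysis) adds: "Slides will be labelled by a unique study participant ID code".
- **Repeat samples.** Section 10.4 states that "all participants will be asked to provide the study team members with additional samples up to 3 times/year", and then again at the next regular appointment. Sections 6.2 and 10.3 instead expect one sampling to be enough for most patients.
- **Use of the repeat call.** The synopsis (Secondary outcome measures) describes re-examining Cx43 in a patient who showed remodelling at first sampling and whose treatment is then changed. "If the new treatment plan results in restoration of Cx43 at the buccal mucosa cell connections", it says, this may point to successful arrhythmia management. The secondary endpoint analysis in section 14 lists the effect of treatment changes on Cx43 among the uses of the present/absent call.
- **Custody of results.** Under section 25 (Data Protection Impact Assessment), the principal investigator (PI) completes the results part of the form that came with the samples. Of the place where forms are kept it says: "The office is locked and accessible only by the PI". Scans sit on a workstation that only the PI can use. Section 12.4 also has observations logged in spreadsheets.
- **Blinding.** Section 6.1 masks the laboratory lead and team to patient details. Section 12.4 denies the PI access to patient data and medical records.

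**The concern.** Restoration of Cx43 is a change within one person, from an earlier abnormal call to a later normal one. Each call is a visual judgement of present or absent, without quantification (section 14.2.1), and no second reader is described. If the earlier call is known, a doubtful slide can be pulled towards it, which hides real change. If the reader also knows that treatment was changed, a doubtful slide can be pulled towards the hoped-for recovery, which creates change that is not there.

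The expectation is already on paper: section 10.4 says that buccal work has shown Cx43 returning under effective anti-arrhythmic medication. The synopsis hopes that the finding could later serve as a non-invasive measure of whether therapy works, so a bias in either direction would matter.

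**Working it through.** The documents give no figure to reproduce. The check is to set the labelling, custody and blinding text side by side.

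1. **Is the ID the same at every sampling?** Section 7 assigns it once, at enrolment. Sections 10.5.1 and 12.4 make it the only identifier on slides, tubes and results. Neither section 10.3 (which describes the home kit) nor section 10.4 mentions a new code for a later sample. That the ID is permanent is inferred from this silence.
2. **What does the label reveal?** It reveals that the slide is a repeat. It does not carry the earlier call; for that, the reader must remember it or look it up.
3. **Can the reader look it up?** The roles statement at the front has the grant holder analyse the samples, manage the data and do the statistics. The Finance section describes the PI as the funded person. Section 25 has the PI complete and hold the forms. Together these suggest that the reader is the PI who holds the earlier results. Names are removed, so this is an inference.
4. **Does a stated safeguard close the route?** The masking in section 6.1 covers patient details. The restriction in section 12.4 covers patient data and medical records. De-identification in section 10.5.1 covers identity. None of them hides a result filed under the same ID, sets a random reading order or holds earlier results back until the new call is made.
5. **Which reads are exposed?** Any second or later read: the Cx43 comparison, the other interim samples and any repeat sub-study sample. A participant's first call has no earlier call behind it.
6. **Which direction?** Anchoring needs only the earlier call. Expecting recovery also needs knowledge of the treatment change, which the ID does not show. The accompanying form lists regular medication (section 25) and could supply it. If Cx43 were re-examined only in those first read as remodelled, as the synopsis describes, the repeat sample would itself hint at an abnormal earlier call. Under section 10.4 everyone is resampled and that hint disappears. The two passages need to be reconciled.
7. **How large?** The excess number called restored would be n × b × (q1 − q0). Here n is the number resampled after an abnormal first call, b the share of their follow-up slides that are borderline, q1 the chance that a borderline slide is called present by a reader who knows the earlier call, and q0 the same chance for a masked reader. The documents give none of the four, and q1 − q0 may have either sign.

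**The case against.** The strongest reply is that nothing shows a reader consulting an earlier result. If a team member other than the PI reads the slides, the locked office keeps the forms from that reader. Restoration of Cx43 is only a potential secondary outcome, section 14.2.2 marks secondary endpoints as not applicable, and the number resampled is unclear. Each of these points stands and limits the concern. None supplies masking: memory remains open to any reader, and no rule keeps the spreadsheets from one. The synopsis calls the qualitative approach free of bias, but a yes/no call does not protect against knowing the previous answer.

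A reader might infer four stronger things that the documents do not support:

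- **The label alone discloses the earlier call.** It shows only that the slide is a repeat.
- **A handful of tipped slides would produce a significant restoration effect.** That needs invented values for the quantities in step 7. If only participants with an absent baseline are followed, every changed call goes one way even under perfect masking, so a small paired p-value would not measure this defect. Nor is a paired test planned: section 14 specifies pairwise Fisher exact tests between disease groups, with Bonferroni correction.
- **Reproducibility would be inflated.** No repeat-read reproducibility analysis is planned.
- **The diagnostic results are compromised.** The first-sample call is not exposed to this route.

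**Conclusion.** The point holds as a gap in masking. One enrolment ID follows the participant through every sample and result, repeat samples are planned, and no text conceals an earlier call from whoever reads the next slide. It is an unprotected opportunity for bias, towards anchoring or, if the treatment change is also known, towards expected recovery. It is confined to the potential Cx43 outcome and other repeat reads.

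The size is unknown and cannot be bounded from the documents. The conclusion assumes that the ID is not changed between samplings. It does not require that the PI is the reader, although that would widen access to earlier results. The sponsor should make the change because it is cheap and alters a stated labelling rule, not because a distortion has been shown.

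**What to change.** - **Labels (sections 7, 10.5.1 including the sub-study text, and 12.4).** Give each sampling occasion a new random code without a site prefix. The direct care team records the link to the participant ID in the log it already holds. Section 6.1 and section 25 confine that key to the care team, while the roles statement at the front opens the linking file to study team members; settle this in favour of the care team, because the masking depends on it.
- **Withholding (section 25).** Keep the accompanying form and all earlier results from the reader until the call is recorded. New codes alone are not enough, because diagnosis, mutation, medication and other conditions on the form could allow repeats to be matched.
- **Interim feedback (section 10.4).** Keep it as it is. The care team links each recorded call through its log as the call arrives, without waiting for batches.
- **Cx43 restoration analysis (section 14).** Re-read the stored baseline and follow-up TIF images under new codes, in random order and mixed with other participants' images. Link them only after all calls are recorded.

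The cost is extra labels, one more column and look-up in the log, and some re-reading. One limit remains: re-reading images masks the final call, but not the original staining or the choice of field that was imaged.

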1.1 Recording Adverse Events (AEs)

No adverse events are anticipated. There is no harm or risk associated with obtaining a buccal smear sample.

All Adverse Events will be recorded in the hospital notes in the first instance. A record of all AEs will also be kept in the CRF and the Sponsor's AE Log JREOLOG0007.

1.2 Investigator Responsibilities relating to Safety Reporting

Collection, recording and reporting of AEs (including serious and non-serious events and reactions) to the Sponsor will be done according to the Sponsor's Safety reporting for non-CTIMP studies SOP JREOSOP0033. All SAEs will be recorded in the hospital notes and the CRF, and the Sponsor's AE Recording Log JREOLOG0007. The AE Log will be sent to the Sponsor on request and every 2 months.

All SAEs will be reported both to the Sponsor via the JREO & REC using the SAE report form for research other than CTIMPs (non-CTIMPs) published on the HRA website. The Chief or Principal Investigator at any participating site will complete the SAE form which will be faxed both to the JREO on [name] or E-mailed to [contact], within 48hrs of the Investigator becoming aware of the event, and via email to the relevant REC.

The Chief or Principal Investigator will respond to any SAE queries raised by the Sponsor as soon as possible. Follow up reports must continually be completed within acceptable time-frames and sent as detailed above until the reportable event is considered resolved.

Events will be followed up until resolution; any appropriate follow-up information will be clearly marked as such and reported to the sponsor via the JREO as above in a timely manner.

Full reports should be completed and submitted to REC within 15 days of the event

